**Figure RHBV.1. Illustration of study design for Clinical Protocol I1F-MC-RHBV.**

## 4.2. End of Trial Definition

End of the trial is the date of the last visit or last scheduled procedure shown in the Schedule of Activities ([Appendix 2](#)) for the last patient in the trial.

## 4.3. Scientific Rationale for Study Design

Two treatment regimens of ixekizumab 80 mg (Q2W and Q4W) will be studied as detailed in Section [6.1](#), and the effect of an 80 mg and a 160 mg starting dose will be evaluated for treatment outcomes. Dose justification is outlined in Section [4.4](#). The study blind is maintained as described in Section [6.3](#).

The placebo-controlled Blinded Treatment Dosing Period (Period 2) is designed to minimize bias in the evaluation of ixekizumab in patients with rad-axSpA for both efficacy and safety. All patients may still receive treatment in the form of the allowed concomitant medications as described in the study inclusion and exclusion criteria (Sections [5.1](#) and [5.2](#)), and concomitant therapy (Section [6.8](#)). Patients can be discontinued from study treatment at any time by investigator or patient decision if they are considered to be receiving insufficient benefit from study treatment (Section [7.1.1](#)).

As of Week 16 (after completion of Period 2) investigators are allowed to adjust some concomitant medications, if needed, as specified in Section [6.8](#), across all treatment groups.

Patients originally assigned to placebo during Period 2 will be rerandomized at a 1:1 ratio to ixekizumab 80 mg Q2W or Q4W with a 160 mg starting dose at Week 16.

Adalimumab 40 mg Q2W will provide the active control for comparison with placebo during Blinded Treatment Dosing Period 2 to determine assay sensitivity in the context of study implementation. Adalimumab has been selected because it is an approved therapy for the treatment of AS (rad-axSpA) in countries in which this study will be conducted, and its approved dosing regimen fits well with the frequency of dosing of ixekizumab regimens in this study.

Patients assigned to adalimumab at Week 0 will have the last adalimumab injection at Week 14, be re-randomized to ixekizumab 80 mg Q2W or Q4W at Week 16, and start ixekizumab at Week 20 to allow a 6-week washout period for safety reasons. The length of the washout period takes into account the half-life of adalimumab (mean terminal half-life is approximately 2 weeks, hence majority of adalimumab will be cleared after 6 weeks), the desire to minimize risk of relapse, and the study visit schedule.

Ixekizumab 80 mg Q2W and 80 mg Q4W treatment regimens are continued beyond Week 16 to further assess safety and efficacy during the Extended Treatment Period (Period 3).

The effectiveness of ixekizumab in treating rad-axSpA will be assessed primarily by the ASAS40 response rate at Week 16. ASAS20 response will also be assessed at Week 16. These measures and the Week 16 endpoint are in alignment with efficacy endpoints for currently approved rad-axSpA therapies and with regulatory guidance (EMA 2009). Steady-state exposure of ixekizumab is expected to be reached by Week 16. Based on previous studies with ixekizumab in patients with psoriasis, RA, and PsA, it is anticipated that maximum or near

maximum clinical effect in rad-axSpA will be achieved within this timeframe for both ixekizumab treatment regimens as well as for the active control treatment group.

Baseline CRP has been reported as a predictor of response in patients with rad-axSpA treated with TNF inhibitors (Inman et al. 2008; de Vries et al. 2009; Sieper et al. 2011; Vastesaeger et al. 2011); hence by including it as a stratification factor, it ensures balance in baseline CRP levels resulting in greater comparability across treatment groups at baseline.

The Extended Treatment Period (Period 3) will permit collection of data for the assessments of maintenance of efficacy and long term safety with ixekizumab.

The Post-Treatment Follow-Up Period (Period 4) is important for safety and efficacy monitoring following administration of the last study treatment.

#### 4.4. Justification for Dose

Lilly considers it appropriate to evaluate 2 treatment regimens in Study RHBV to enable appropriate evaluation of the relative benefit/risk associated with continuous ixekizumab therapy in axSpA.

CCI [REDACTED]

As referred to above, the current internal (ixekizumab) and external (TNF inhibitors and secukinumab) scientific data in this area support the rationale for studying ixekizumab in patients with rad-axSpA with the proposed treatment regimens.

#### 4.5. Benefit/Risk Assessment

More information about the known and expected benefits, risks, serious adverse events (SAEs) and reasonably anticipated adverse events (AEs) of ixekizumab are to be found in the IB.

## 5. Study Population

The study population will include patients with active rad-axSpA (with sacroiliitis defined radiographically according to the modified New York [mNY] criteria, based on central reading, associated with at least 1 SpA feature [Appendix 5]), who have given written informed consent.

Study investigator(s) will review patient history and screening test results from Visit 1 (all criteria), and Visit 2 as per the Schedule of Activities (Appendix 2) to determine if the patient meets all inclusion and none of the exclusion criteria to qualify for participation in the study. All screening activities must be completed and reviewed before the patient is randomized. Patients may be rescreened in the circumstances described in Section 5.3.

Prospective approval of protocol deviations to recruitment and enrollment criteria, also known as protocol waivers or exemptions, are not permitted.

In this protocol section, the following definitions apply:

- Screening is defined as Visit 1, up to 42 days prior to baseline randomization.
- Baseline randomization visit is defined as Visit 2 (Week 0).

### 5.1. Inclusion Criteria

Patients are eligible to be included in the study only if they meet all of the following criteria at screening or as specified:

#### Type of Patient and Disease Characteristics

- [1] Have an established diagnosis of rad-axSpA with sacroiliitis defined radiographically according to the mNY criteria (van der Linden et al. 1984) based on central reading: sacroiliitis grade  $\geq 2$  bilaterally or grades 3 to 4 unilaterally.  
  
AND  
  
At least 1 SpA feature, according to ASAS criteria (Rudwaleit et al. 2009; Sieper et al. 2009), listed in Appendix 5.
- [2] Patients have a history of back pain  $\geq 3$  months with age at onset  $< 45$  years
- [3] Have active rad-axSpA defined as BASDAI  $\geq 4$  and total back pain  $\geq 4$  (Sieper et al. 2009, Box 25 Spinal Pain) on an NRS at screening and baseline.
- [4] Must have had an inadequate response, as determined by the investigator, to 2 or more NSAIDs at the therapeutic dose range for a total duration of at least 4 weeks OR have a history of intolerance to NSAIDs.
- [5] Patients must have a history of prior therapy for axSpA of at least 12 weeks prior to screening. Examples of prior therapy may include but are not limited to physical therapy and NSAID treatment.
- [6] If taking NSAIDs or cyclooxygenase-2 (COX-2) inhibitors, the dose must be stable for at least 2 weeks prior to baseline randomization.

**Patient Characteristics**

[7] Are ambulatory male or female patients  $\geq 18$  years of age at time of screening.

[8] Must agree to use a reliable method of birth control

- If a male patient, patient agrees to use a reliable method of birth control during the study and for at least 12 weeks following the last dose of investigational product, whichever is longer. Methods of birth control include, but are not limited to, condoms with spermicide and male sterilization.

OR

- If a female patient is a woman of childbearing potential who tests negative for pregnancy and agrees to use a reliable method of birth control or remain abstinent during the study and for at least 12 weeks following the last dose of investigational product, whichever is longer. Methods of contraception include, but are not limited to:

oral contraceptives, contraceptive patch, injectable or implantable contraceptives, intrauterine device, vaginal ring, diaphragm with contraceptive gel, or condom with contraceptive foam.

OR

- If a female patient is a woman of nonchildbearing potential, she is not required to use any method of birth control. Nonchildbearing potential is defined as:

Women who have had surgical sterilization (hysterectomy or bilateral oophorectomy or tubal ligation).

- or -

Women who are  $\geq 60$  years of age.

- or -

Women  $\geq 40$  and  $< 60$  years of age who have had a cessation of menses for  $\geq 12$  months and a follicle stimulating hormone (FSH) test confirming nonchildbearing potential ( $\geq 40$  mIU/mL or  $\geq 40$  IU/L).

**Informed Consent**

[9] Have given written informed consent approved by Lilly, or its designee, and the Investigational Review Board (IRB)/Ethical Review Board (ERB) governing the site.

**5.2. Exclusion Criteria**

Patients will be excluded from study enrollment if they meet any of the following criteria at screening or as specified:

**Medical Conditions**

- [10] Have total ankylosis of the spine, as assessed locally, based on lateral radiographs of the cervical and lumbar spine.
- [11] Have any condition or contraindication as addressed in the local labeling for adalimumab that would preclude the patient from participating in this protocol.
- [12] Have a history of other systemic inflammatory diseases (such as but not limited to: lupus, vasculitis or RA), or other chronic pain conditions (such as but not limited to fibromyalgia) that might confound the evaluations of benefit from ixekizumab therapy.

**Note:** Patients with psoriasis that have never received and do not require systemic treatment for psoriasis, such as but not limited to oral agents or biologic therapies, can be included provided these patients fulfill the entry criteria.

- [13] Have active Crohn's disease (CD) or active ulcerative colitis (UC).

**Note:** Patients may be enrolled if they have had a history of IBD, including CD and UC, but have had no exacerbation for  $\geq 6$  months prior to baseline randomization and, if currently on treatment, must be on stable treatment for  $\geq 6$  months prior to baseline randomization.

- [14] Have evidence of active anterior uveitis (an acute episode) within the last 4 weeks prior to baseline randomization.

**Note:** These patients may be rescreened only one time  $\geq 4$  weeks after resolution of acute symptoms.

- [15] Have current or a history of lymphoproliferative disease, or signs or symptoms of lymphoproliferative disease within 5 years prior to baseline randomization; or have active or history of malignant disease within 5 years prior to baseline randomization.
- [16] Have a history of fluid overload, myocardial infarction (MI), uncompensated heart failure, or evidence of new-onset ischemic heart disease or in the opinion of the investigator other serious cardiac disease, within 12 weeks prior to baseline randomization.
- [17] Presence of significant uncontrolled cerebrocardiovascular events (for example, unstable angina, unstable arterial hypertension, moderate-to-severe heart failure [New York Heart Association class III/IV], or cerebrovascular accident) at screening that, in the opinion of the investigator, pose an unacceptable risk to the patient if participating in the study or of interfering with the interpretation of data.

- [18] Presence of any comorbid respiratory, hepatic, renal, gastrointestinal, endocrine, hematologic disorders, at screening that, in the opinion of the investigator, pose an unacceptable risk to the patient if participating in the study or of interfering with the interpretation of data.
- [19] Presence of any neurologic or neuropsychiatric disorders, at screening that, in the opinion of the investigator, poses an unacceptable risk to the patient if participating in the study or of interfering with the interpretation of data.
- [20] Presence of significant uncontrolled neuropsychiatric disorder; have recent history (within 30 days prior to screening visit [Visit 1] and any time between screening visit [Visit 1] and baseline randomization [Visit 2]) of a suicide attempt; or have a score of 3 on Item 12 (Thoughts of Death or Suicide) of the Quick Inventory of Depressive Symptomatology-self report (16 items) (QIDS-SR16) at screening or baseline randomization or are clinically judged by the investigator to be at risk for suicide.
- [21] Have presence or personal history or family history (1st degree relative) of demyelinating disorder.
- Note:** 1st degree means child, parent, or sibling, provided a blood relationship exists.
- [22] Patients who have:
- in the past 12 weeks prior to baseline randomization:
    - had a serious infection (for example, pneumonia, cellulitis),
    - have been hospitalized for an infection,
    - or have received intravenous (IV) antibiotics for an infection,
  - or in the past 24 weeks prior to baseline randomization had a serious bone or joint infection
  - or have ever had,
    - an infection of an artificial joint,
    - an infection that occurs with increased incidence in an immunocompromised host (including, but not limited to, Pneumocystis jirovecii pneumonia, symptomatic histoplasmosis, or coccidioidomycosis)
- [23] Have a known immunodeficiency or are immunocompromised to an extent such that participation in the study would pose an unacceptable risk to the patient.
- [24] Have or had a herpes zoster or any other clinically apparent varicella-zoster virus infection within 12 weeks of baseline randomization.

- [25] Have any other active or recent infection within 4 weeks of baseline randomization that in the opinion of the investigator, would pose an unacceptable risk to the patient if participating in the study.
- Note:** These patients may be rescreened one time  $\geq 4$  weeks after resolution of symptoms.
- [26] Have known allergy to rubber or latex.
- [27] Have a known allergy or hypersensitivity to any biologic therapy that would pose an unacceptable risk to the patient if participating in this study.
- [28] Have had surgical treatment of a joint that is to be assessed in the study within 8 weeks prior to baseline randomization or will require surgical treatment of a joint that is to be assessed in the study during the first 16 weeks of the trial.
- [29] Have had any major surgery within 8 weeks prior to baseline randomization, or will require major surgery during the study that in the opinion of the investigator and in consultation with Lilly or its designee would pose an unacceptable risk to the patient.

#### **Prior/Concurrent Therapy or Clinical Trial Experience**

- [30] Have received cDMARDs and/or other therapies such as but not limited to: gold salts, cyclosporine, azathioprine, dapsone, 6-mercaptopurine, mycophenolate mofetil, or any other immunosuppressive agents within 4 weeks prior to baseline randomization.

Exception: MTX (oral or parenteral up to 25 mg/week), sulfasalazine (up to 3 g/day), or hydroxychloroquine (up to 400 mg/day) may be allowed IF at stable dose for at least 4 weeks prior to baseline randomization.

AND

if used, must not be in any combination with other cDMARDs.

**Note:** If MTX is used, local standard of care is to be followed for concomitant administration of folic or folinic acid with MTX.

- [31] Use of oral corticosteroids  $>10$  mg/day prednisone or its equivalent.
- Note:** If patients are taking prednisone or its equivalent and the dose is  $\leq 10$  mg/day, the dose must be stable for at least 4 weeks prior to baseline randomization.
- [32] Have received any prior, or are currently receiving, treatment with biologic or other immunomodulatory agents, including investigational therapies (such as but not limited to Janus kinase (JAK) inhibitors, TNF inhibitors, IL-1, IL-6, IL-23, IL-17 (including ixekizumab), IL-17R, T cell, or B cell targeted therapies).

[33] Are currently enrolled in, have participated, or discontinued from a clinical trial involving an investigational product or nonapproved use of a drug or device within the last 30 days prior to screening or a period of at least 5 half-lives of the last administration of the drug, whichever is longer.

**Note:** Investigational products that are biologic or other immunomodulatory agents are not permitted regardless of washout period (described in criterion above).

[34] Are currently enrolled in any other clinical trial involving an investigational product or any other type of medical research judged not to be scientifically or medically compatible with this study.

[35] Are currently receiving or have received treatment with denosumab within 6 months prior to baseline randomization.

[36] Have received any parenteral glucocorticoid administered by intra-articular, intramuscular, or IV injection within 6 weeks prior to baseline randomization, or for whom a parenteral injection of glucocorticosteroids is anticipated during the Blinded Treatment Dosing Period (Period 2) of the study.

[37] Use of any opiate analgesic at average daily doses >30 mg/day of morphine or its equivalent or use of variable doses of any opiate analgesic within 6 weeks prior to baseline randomization. Exception for patients with pain that may interfere with undergoing an MRI: patient may receive premedication of ≤30 mg of morphine or equivalent, on the day of the MRI, for significant pain as judged by the investigator.

[38] Had a live vaccination within 12 weeks prior to baseline randomization, or intend to have a live vaccination during the course of the study, or within 12 weeks of completing treatment in this study, or have participated in a vaccine clinical study within 12 weeks prior to baseline randomization. Investigators are to review the vaccination status of their patients and follow the local guidelines for adult vaccination with nonlive vaccines intended to prevent infectious disease prior to therapy.

**Note:** Killed/inactive or subunit vaccines are expected to be safe; however, their efficacy with concomitant ixekizumab treatment is unknown.

[39] Had a vaccination with Bacillus Calmette-Guérin (BCG) within 12 months prior to baseline randomization, or intend to have this vaccination with BCG during the course of the study, or within 12 months of completing treatment in this study.

### Diagnosics Assessments

[40] Have a body temperature  $\geq 38^{\circ}\text{C}$  ( $100.5^{\circ}\text{F}$ ) at baseline randomization.

**Note:** These patients may be rescreened one time  $\geq 4$  weeks after documented resolution of elevated temperature.

- [41] Have evidence or suspicion of active or latent TB (refer to Section 5.3 for rescreening and Section 8.4.6 for details on determining full TB exclusion criterion).
- [42] Are positive for human immunodeficiency virus serology (HIV); that is, positive for human immunodeficiency virus antibody (HIVAb).
- [43] Have evidence of or test positive for hepatitis B virus (HBV) by testing positive for: 1) HBV surface antigen (HBsAg+), OR 2) anti-hepatitis B core antibody positive (HBcAb+) and are HBV DNA positive.

**Note:** Patients who are HBcAb+ and HBV DNA negative may be enrolled in the study. Patients who meet these criteria at screening will be identified by the central laboratory and monitored during the study as detailed in Section 8.4.10.2.

- [44] Have evidence of or test positive for hepatitis C virus (HCV). A positive test for HCV is defined as: 1) positive for hepatitis C antibody (anti-HCV Ab); and 2) positive via a confirmatory test for HCV (for example, HCV-polymerase chain reaction).
- [45] Have electrocardiogram (ECG) abnormalities that are considered clinically significant and would pose an unacceptable risk to the patient if participating in the study.
- [46] Patients having contraindications to MRI (for example, claustrophobia, pacemakers, aneurysm clips, intraocular metallic fragments).

**Note:** For claustrophobia, premedication with benzodiazepine is allowed (investigator should assess for potential interactions with other concomitant medication(s) such as opiates).

**Laboratory tests may not be repeated unless there is a technical error or clinical reason to believe a result may need to be retested within the screening period.** Laboratory tests can be repeated a maximum of 1 time, and results must be received and reviewed prior to randomization. For eligibility, the most recent lab panel must not meet any of the following criteria:

- [47] At screening, have a neutrophil count  $<1500$  cells/ $\mu\text{L}$  ( $<1.50 \times 10^3/\mu\text{L}$  or  $<1.50$  GI/L).
- [48] At screening, have a lymphocyte count  $<800$  cells/ $\mu\text{L}$  ( $<0.80 \times 10^3/\mu\text{L}$  or  $<0.80$  GI/L).
- [49] At screening, have a platelet count  $<100,000$  cells/ $\mu\text{L}$  ( $<100 \times 10^3/\mu\text{L}$  or  $<100$  GI/L).
- [50] At screening, have aspartate aminotransferase (AST) or alanine aminotransferase (ALT)  $>2.5$  times the upper limit of normal ( $>2.5 \times \text{ULN}$ ).
- [51] At screening, have a total white blood cell (WBC) count  $<3000$  cells/ $\mu\text{L}$  ( $<3.00 \times 10^3/\mu\text{L}$  or  $<3.00$  GI/L).

- [52] At screening, have hemoglobin <8.5 g/dL (85.0 g/L) for male patients and <8.0 g/dL (80 g/L) for female patients.
- [53] Have other clinical laboratory test results at screening that are outside the normal reference range for the population and are considered clinically significant, per investigator assessment.

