#### **8.4.10.2. Hepatitis B Monitoring**

Patients that are HBcAb+ at screening, regardless of other hepatitis B testing results, will have a serum HBV DNA specimen obtained to be analyzed by the central laboratory. Such patients that are determined to be HBV DNA negative (undetectable) may be enrolled into the study with required HBV DNA monitoring every 3 to 4 months during treatment and 12 weeks after the last dose of ixekizumab. Patients that are found to be HBV DNA positive (detectable) at screening will be excluded from the trial.

If the result of any subsequent HBV DNA testing is positive, the patient is to be discontinued from the study treatment, is to continue safety follow up, and is to receive appropriate follow-up medical care, including consideration for antiviral therapy. A specialist physician in the care of patients with hepatitis (for example, infectious disease or hepatologist subspecialists) is to be consulted and potentially start antiviral therapy prior to discontinuation of any immunosuppressant or immunomodulatory therapy (including investigational drug). Timing of discontinuation from the study and of any immunosuppressant/immunomodulatory therapy

(including investigational product) needs to be based on the recommendations of the consulting specialist physician in conjunction with the investigator and medical guidelines/standard of care.

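### Section 8.4.10.2 and SAP deviation row [43] do not carry the stand-alone HBsAg limb of exclusion [43], which governs: a low-severity consistency correction

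*Protocol*

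**What the plan says.** **The rule.** Protocol Section 5.2, criterion [43], excludes on either of two limbs: "Have evidence of or test positive for hepatitis B virus (HBV) by testing positive for: 1) HBV surface antigen (HBsAg+), OR 2", where the second limb is HBcAb positivity combined with a positive HBV DNA result. Section 5.2 opens with "Patients will be excluded from study enrollment if they meet any of the following criteria at screening or as specified". Section 5 asks the investigator to confirm that the patient "meets all inclusion and none of the exclusion criteria to qualify for participation in the study", and says that prospective deviations from the entry criteria, "also known as protocol waivers or exemptions, are not permitted". Appendix 3 (footnote f) lists HBsAg among the Visit 1 tests that decide eligibility.

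**The permission.** Section 8.4.10.2 begins: "Patients that are HBcAb+ at screening, regardless of other hepatitis B testing results, will have a serum HBV DNA specimen obtained". Its next sentence gives the permission: "Such patients that are determined to be HBV DNA negative (undetectable) may be enrolled into the study". Repeat DNA testing, on treatment and once after the final dose, is attached to that permission. No HBsAg condition appears there. The Note under [43] says "Patients who are HBcAb+ and HBV DNA negative may be enrolled in the study" and is silent on HBsAg. Appendix 2 footnote s gives a similar permission, but the result it sets aside is HBsAb, the surface antibody, and not the antigen.

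**The deviation row.** SAP Section 6.15, Table RHBV.6.12, row [43] names evidence of HBV, or a positive HBV test, joined to a positive HBV DNA result. HBsAg is not mentioned as sufficient by itself. The row's action keeps such patients in the per-protocol set. Its source is both the site monitor and statistical programming, and footnote a says that either source is enough.

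**The concern.** The eligibility rule is an OR: surface antigen alone excludes. Section 8.4.10.2 restates eligibility through core antibody and DNA only. The SAP row turns the OR into a rule that always needs DNA positivity.

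Two things are at stake. A site that reads Section 8.4.10.2 by itself could take it as a carve-out for an HBsAg-positive patient whose DNA is undetectable, in a trial of two immunomodulating biologics. And SAP Section 6.15 counts as important those deviations that may significantly affect a patient's rights, safety or well-being. If row [43] were applied as labelled, an excluded HBsAg-positive patient without positive DNA would not appear under it.

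**Working it through.** The plan gives no figure to reproduce on this point. The check lists the possible screening results and applies each text to them.

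**Inputs**
- [43]: exclude if HBsAg+, or if HBcAb+ and HBV DNA+.
- Section 8.4.10.2, read alone: enrolment permitted if HBcAb+ and HBV DNA negative.
- SAP row [43], natural reading: a positive HBV test (HBsAg+ or HBcAb+) and HBV DNA+.
- Appendix 3 footnote g: HBV DNA is tested only in patients who are HBcAb+ at screening.

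**Number of profiles.** HBsAg has 2 states. HBcAb+ splits into 2 DNA states, and HBcAb-negative gives 1 (not tested). That makes 2 × (2 + 1) = 6.

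| HBsAg | HBcAb | HBV DNA | [43] excludes | 8.4.10.2 alone permits | SAP row describes |
|---|---|---|---|---|---|
| + | + | + | yes | no | yes |
| + | + | neg | **yes** | **yes** | **no** |
| + | neg | not tested | **yes** | silent | **no** |
| neg | + | + | yes | no | yes |
| neg | + | neg | no | yes | no |
| neg | neg | not tested | no | silent | no |

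**Counts**
- [43] excludes 3 HBsAg+ profiles plus 1 HBsAg-negative profile, which is 4 of 6.
- Section 8.4.10.2 permits 2. Exclusion and permission overlap in 1: HBsAg+/HBcAb+/DNA-negative.
- The SAP row describes 2 of the 4 excluded profiles and omits 4 − 2 = 2: HBsAg+/HBcAb+/DNA-negative and HBsAg+/HBcAb-negative. The second is never DNA tested, so it could not satisfy the row.
- On-treatment HBV DNA monitoring follows HBcAb+/DNA-negative patients. It would reach 1 of the 2 omitted profiles and would miss HBsAg+/HBcAb-negative.

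**Sensitivity to the testing rule.** If DNA were known for everyone there would be 2 × 2 × 2 = 8 combinations. [43] would exclude 4 + 1 = 5 and the SAP row would describe 3, so it would still omit 2. The overlap with Section 8.4.10.2 would still be 1.

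**After the fix.** Limiting the permission to HBsAg-negative patients leaves one permitted profile, HBsAg-negative/HBcAb+/DNA-negative, so the overlap goes from 1 to 0. Restating [43] in the SAP row takes the omitted profiles from 2 to 0. That second zero follows by construction, because the row then is the criterion.

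**The case against.** The strongest reply is that there is no operative conflict. [43] governs, any single exclusion suffices, waivers are barred and HBsAg is a mandatory Visit 1 test. A statement that patients may be enrolled does not lift another exclusion. This stands: a reader might infer that the protocol admits HBsAg-positive patients, or contains two rules that cannot be reconciled, and the documents support neither.

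Next, the clause setting aside other HBV results attaches grammatically to drawing the DNA sample. That is so, but the next sentence carries the same group into the enrolment permission, so the mismatch in Section 8.4.10.2 remains. A reader might extend it to the Note under [43] and to footnote s. That goes too far: the Note sits inside [43] and states the complement of its second limb, and footnote s sets aside only the antibody.

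On the SAP, the rows are short labels, and others are also narrower than their criteria: row [1] does not name the required SpA feature, and row [7] drops the ambulatory condition. It is tempting to contrast row [43] with the hepatitis C row [44], which is broader than its criterion, but that comparison is selective and shows nothing about intent. A reader might also infer that the programmed check misses these patients. The detailed specification sits outside these documents, so that cannot be known. A monitor applying protocol [43] could still record the deviation.

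Finally, other safeguards exist. Section 7.1.2 deals with inadvertent enrolment. Exclusions [18] and [53] can catch hepatic disorders and clinically significant laboratory findings. Serial chemistry and the hepatic discontinuation criteria apply to all patients, and criterion [13] stops treatment if HBV DNA becomes positive. No text permits enrolment of an HBsAg+/HBcAb-negative patient, so that case requires a site to disregard a positive eligibility test. All of this lowers the weight of the point without removing the two mismatches.

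**Conclusion.** The point holds as a low-severity consistency correction. [43] bars every HBsAg-positive patient. Section 8.4.10.2, on its own terms, contradicts it for one screening profile, and SAP row [43] as worded leaves out two of the four excluded profiles.

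This rests on two readings: that the permission in Section 8.4.10.2 inherits the whole group defined in the sentence before it, and that the DNA condition in the SAP row applies to the whole label. A looser parse, in which evidence of HBV counts by itself, would cover surface-antigen positivity, but it is not the natural reading.

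The effect is limited to clarity of safety eligibility and completeness of deviation reporting. A reader might suspect an effect on the results. There is none: the ITT population takes all randomized patients, row [43] does not remove anyone from the per-protocol set, and power is untouched. The counts are wording cases; the number of patients affected is unknown and may be zero. SAP Version 3 was approved after unblinding, which follows the last patient's Week 16 visit, so by then a protocol edit could no longer change who enrolled. The deviation row can still matter for reporting.

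**What to change.** - **Protocol Section 8.4.10.2:** limit the enrolment permission to patients who are HBsAg-negative, HBcAb+ and HBV DNA negative.
- **SAP Table RHBV.6.12, row [43]:** word and program it as HBsAg+, or HBcAb+ and HBV DNA positive.
- **Optional, for consistency:** add HBsAg-negative to the Note under [43] and to Appendix 2 footnote s.

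The cost is a few words in one protocol section and one SAP row, plus a check that the programmed deviation uses the HBsAg result. No new test is needed, because HBsAg is already measured at Visit 1 for eligibility.
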